#### Intensity of adverse event

The intensity of the AE should be judged based on the following:

Mild:	Awareness of sign(s) or symptom(s) which is/are easily tolerated
Moderate:	Enough discomfort to cause interference with usual activity
Severe:	Incapacitating or causing inability to work or to perform usual activities

#### Pregnancy:

In rare cases, pregnancy might occur in this study. Once a subject has been enrolled into the study with Spiolto® Respimat®, the investigator must report any drug exposure during pregnancy, which occurred in a female subject or in a partner to a male subject, to the Sponsor by means of Part A of the Pregnancy Monitoring Form. The outcome of the pregnancy associated with the drug exposure during pregnancy must be followed up and reported by means of Part B of the Pregnancy Monitoring Form.

In the absence of a reportable AE, only the Pregnancy Monitoring Form must be completed, otherwise the NIS AE form is to be completed and forwarded (by fax) to the local Pharmacovigilance point of contact for each country within respective timelines.

#### Expedited Reporting of ADRs / Fatal AEs and Drug Exposure During Pregnancy

The following must be reported by the investigator on the NIS (S)AE Form from signing the informed consent onwards until the end of the study:

Table 11.2:1 Reporting types and timelines

Type of Report*	Timeline
All SADRs associated with Spiolto ® Respimat ®	immediately within 24 hours
All AEs with fatal outcome in patients exposed to Spiolto ® Respimat ®	immediately within 24 hours
All non-serious ADRs associated with Spiolto ® Respimat ®	7 calendar days
All pregnancy monitoring forms associated with Spiolto ® Respimat ®	7 calendar days

The same timelines apply if follow-up information becomes available for the respective events. In specific occasions the Investigator could inform the Sponsor upfront via telephone. This does not replace the requirement to complete and fax/email the NIS (S)AE form.

#### Information required

For each reportable adverse event, the investigator should provide the information requested on the appropriate (e)CRF pages and the NIS (S)AE form.

#### Reporting of related Adverse Events associated with any other BI drug

The investigator is encouraged to report all adverse events related to any BI drug other than the Spiolto® Respimat® according to the local regulatory requirements for spontaneous AE reporting at the investigator's discretion by using the locally established routes and AE report forms. The term AE includes drug exposure during pregnancy, and, regardless of whether an AE occurred or not, any abuse, off-label use, misuse, medication error, occupational exposure, lack of effect, and unexpected benefit.

### **11.3 REPORTING TO HEALTH AUTHORITIES**

Adverse event reporting to regulatory agencies will be done by the Sponsor according to local and international regulatory requirements.

## **12. PLANS FOR DISSEMINATING AND COMMUNICATING STUDY RESULTS**

Results of this non-interventional study will be disclosed on [encepp.eu](http://encepp.eu) and [clinicaltrials.gov](http://clinicaltrials.gov) and a study specific publication plan will be developed to describe planned publications.

## **ANNEX 1. LIST OF STAND-ALONE DOCUMENTS**

The stand-alone documents for this non-interventional study are:

- Informed Consent Form
- Physicians' Global Evaluation (PGE)
- PF-10 Questionnaire based on SF-36
- Breathlessness Scale (mMRC)
- Patient Satisfaction Survey
- Statistical Epidemiological Analysis Plan (SEAP)
- Data Management Plan (DMP)
- Pregnancy Monitoring Form
- Serious Adverse Event Report in Non-Interventional Studies (NIS (S)AE Form)
- Publication Plan

All of the above documents will be archived in the Trial Master File in its original English master version.

## **ANNEX 2. ENCEPP CHECKLIST FOR STUDY PROTOCOLS**

Not applicable.

### ANNEX 3. ADDITIONAL INFORMATION

#### Physical Functioning Questionnaire (PF-10) based on the 36-Item Short Form Survey.

Please circle one number on each line.

	Yes, Limited a Lot	Yes, Limited a Little	No, Not limited at All
1. Vigorous activities , such as running, lifting heavy objects, participating in strenuous sports	[1]	[2]	[3]
2. Moderate activities , such as moving a table, pushing a vacuum cleaner, bowling, or playing golf	[1]	[2]	[3]
3. Lifting or carrying groceries	[1]	[2]	[3]
4. Climbing several flights of stairs	[1]	[2]	[3]
5. Climbing one flight of stairs	[1]	[2]	[3]
6. Bending, kneeling, or stooping	[1]	[2]	[3]
7. Walking more than a mile	[1]	[2]	[3]
8. Walking several blocks	[1]	[2]	[3]
9. Walking one block	[1]	[2]	[3]
10. Bathing or dressing yourself	[1]	[2]	[3]

**Modified Medical Research Council (mMRC) dyspnea (breathlessness) scale**

**Please circle the number which best describes your grade of breathlessness.**

I only get breathless with strenuous exercise. 0

I get short of breath when hurrying on level ground or walking up a slight hill. 1

On level ground, I walk slower than people of the same age because of breathlessness, or have to stop for breath when walking at my own pace. 2

I stop for breath after walking about 100 yards or after a few minutes on level ground. 3

I am too breathless to leave the house or I am breathless when dressing. 4

**Patient Satisfaction Questionnaire**

**Please circle the number which best describes your satisfaction with Spiolto® Respimat®.**

**What is your overall satisfaction with the Spiolto® Respimat® treatment?**

1	2	3	4	5	6	7
very dissatisfied	dissatisfied	rather dissatisfied	neither satisfied nor dissatisfied	rather satisfied	satisfied	very satisfied

**How satisfied are you with inhaling from the Respimat® device (e.g. feeling of inhalation, ease of inhalation, speed of inhalation)?**

1	2	3	4	5	6	7
very dissatisfied	dissatisfied	rather dissatisfied	neither satisfied nor dissatisfied	rather satisfied	satisfied	very satisfied

**How satisfied are you with the handling of the Respimat® inhalation device?**

1	2	3	4	5	6	7
very dissatisfied	dissatisfied	rather dissatisfied	neither satisfied nor dissatisfied	rather satisfied	satisfied	very satisfied

**Physicians' Global Evaluation (PGE) to be used directly within the eCRF**

General condition of the patient at the initial examination (Visit 1)

Please mark with a cross as applicable

Poor	Satisfactory	Good	Excellent
 1  2	 3  4	 5  6	 7  8

General condition of the patient after approximately 6 weeks of treatment (Visit 2)

Please mark with a cross as applicable

Poor	Satisfactory	Good	Excellent
 1  2	 3  4	 5  6	 7  8

2. LIST OF ABBREVIATIONS

Term	Definition / description
AE	Adverse event
BI	Boehringer Ingelheim Pharma GmbH&Co. KG
CR	Complete Response
COPD	Chronic obstructive lung disease
GOLD	Global Initiative for Chronic Obstructive Lung Disease
LABA	Long-acting beta2-adrenoceptor agonist
LAMA	Long-acting anticholinergic bronchodilator
Max	Maximum
MedDRA	Medical Dictionary for Drug Regulatory Activities
Min	Minimum
mMRC	Modified Medical Research Council Scale
NIS	Non-interventional study
PF-10	Physical functioning questionnaire
PGE	Physician's global Evaluation
SAE	Serious Adverse event
TEAE	Treatment-emergent AE
TSAP	Trial Statistical Analysis Plan

3. INTRODUCTION

As per ICH E9^[1], the purpose of this document is to provide a more technical and detailed elaboration of the principal features of the analysis described in the protocol, and to include detailed procedures for executing the statistical analysis of the primary and secondary variables and other data.

This TSAP assumes familiarity with the Clinical Trial Protocol (CTP), including Protocol Amendments. In particular, the TSAP is based on the planned analysis specification as written in CTP Section 9 “Statistical Methods and Determination of Sample Size”. Therefore, TSAP readers may consult the CTP for more background information on the study, e.g., on study objectives, study design and population, treatments, definition of measurements and variables, planning of sample size, randomization.

SAS[®] Version 9.4 or higher will be used for all analyses.

4. CHANGES IN THE PLANNED ANALYSIS OF THE STUDY

- New analyses set, which is not mentioned in the protocol (Details are displayed in Section 6.3):
 - Full analysis set (FAS)

- Further additional analyses, which are not mentioned in the protocol (Details are displayed in Section 7.4)
 - 95% confidence intervals for changes from baseline in PF-10 score

5. ENDPOINT(S)

5.1 PRIMARY ENDPOINT(S)

The primary endpoint of the presented study is “therapeutic success” at visit 2 i.e. approximately 6 weeks after starting treatment, defined as 10-point increase in the PF-10 score between visit 1 and visit 2.

5.2 SECONDARY ENDPOINT(S)

- Absolute changes in PF-10 score from visit 1 to visit 2
- General condition of the patient, evaluated by the physician (PGE score) at visit 1 and visit 2
- Patient satisfaction with Spiolto[®] Respimat[®] at visit 2

5.3 FURTHER ENDPOINT(S)

None.

5.4 OTHER VARIABLE(S)

Other variables will be baseline characteristics and patient’s characteristics such as age, gender, height and weight. Additionally information about concomitant medication, diseases, therapy data, further therapies and comorbidities will be collected as well as about smoking status, exacerbation history, mMRC and GOLD group.

6. GENERAL ANALYSIS DEFINITIONS

6.1 TREATMENT(S)

In the presented study, treatment with Spiolto[®] Respimat[®] will be according to product information.

6.2 IMPORTANT PROTOCOL VIOLATIONS

Table 6.2: 1 defines the different categories of important protocol violations (PVs). The final column describes which PVs will be used to exclude subjects from the different patient analysis sets^[2].

Table 6.2: 1 Important protocol violations

Category/ Code	Description	Requirements	Excluded from
A	Entrance criteria not met		
A1.1	Inclusion criterion 2 (Age >=40 years)	Not met as specified in the protocol	None
A1.2	Inclusion criterion 3 (Patients diagnosed with COPD and requiring long-acting dual bronchodilation (LAMA+LABA) treatment according to approved Spiolto [®] Respimat [®] SmPC and COPD GOLD guideline recommendation)	Not met as specified in the protocol	None
A2.1	Exclusion criterion 1 (Patients with contraindications according to Spiolto [®] Respimat [®] SmPC)	Met as specified in the protocol	None
A2.2	Exclusion criterion 2 (Patients who have been treated with a LABA/LAMA combination (free and fixed dose) in the previous 6 weeks)	Met as specified in the protocol	None
A2.3	Exclusion criterion 3 (Patients continuing LABA-ICS treatment should not be additionally treated with Spiolto [®] Respimat [®] in order to avoid a double dosing of long-acting beta-agonists)	Met as specified in the protocol	None
A2.4	Exclusion criterion 4 (Patients for whom further follow-up is not possible at the enrolling site during the planned study period of approx.. 6 weeks)	Met as specified in the protocol	None
A2.5	Exclusion criterion 5 (Pregnancy and lactation)	Met as specified in the protocol	None
A2.6	Exclusion criterion 6 (Patients currently listed for lung transplantation)	Met as specified in the protocol	None
A2.7	Exclusion criterion 7 (Current participation in any clinical trial or any other non-interventional study of a drug or device)	Met as specified in the protocol	None
B	Informed consent		
B1	Informed consent not available/not done (Inclusion criterion 1)	IC 01 not met as specified in the protocol or informed consent date missing	All

6.3 PATIENT SETS ANALYSED

Full analysis set (FAS): All screened patients with informed consent, date of registration, at least one documented administration of Spiolto[®] Respimat[®] and available PF-10 score at visit 1 and visit 2.

Treated set (TS): All screened patients with informed consent, date of registration and at least one documented administration of Spiolto[®] Respimat[®].

Table 6.3: 1 Patient sets analysed

Class of endpoint	Patient set	
	TS	FAS
Primary and secondary endpoints		X
Safety endpoints	X	
Demographic/baseline	X	

6.5 POOLING OF CENTRES

This section is not applicable because centre/country is not included in the statistical model.

6.6 HANDLING OF MISSING DATA AND OUTLIERS

In context of PF-10 questionnaire, missing values will be replaced with the mean of the other values, if less than half of the questions are missing for a patient. If half or more than half of the questions are missing, no score will be calculated and the PF-10 score will be marked as missing. No other missing data will be imputed.

6.7 BASELINE, TIME WINDOWS AND CALCULATED VISITS

Baseline visit (Visit 1) will include historical and demographic data as well as registration and initial examination. Treatment with Spiolto[®] Respimat[®] will be documented at visit 2 after approximately 6 weeks of treatment.

The mMRC breathlessness scale is completed by the patient at visit 1 and PF-10 questionnaire at visit 1 and 2 as well as satisfaction survey at visit 2. In addition, the PGE is completed by the physician at visit 1 and visit 2.

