## 9. RESEARCH METHODS

### 9.1 STUDY DESIGN

This is a self-controlled study design enrolling consented COPD patients who will be treated with Spiolto® Respimat® according to the approved SmPC.

Patients will be enrolled consecutively and will be followed over an observational period of approx. 6 weeks. Data as listed in [Table 9.1:1](#) will be collected.

Table 9.1:1: Visit flow chart and data collection parameters

Parameter	Visit 1; baseline visit	Visit 2; approx. 6 weeks after baseline visit
Informed Consent	X	
Inclusion / Exclusion Criteria	X	
Patient demographics (age, gender, height, and weight)	X	
Smoking history	X	X
Start of COPD	X	
Number of exacerbations in the last 12 months	X	
Number of exacerbations leading to hospitalization in the last 12 months	X	
Past COPD therapies (6 months before Visit 1)	X	
COPD related and other relevant concomitant medication	X	X
Concomitant diseases / Comorbidities	X	X
Respimat ® training (yes/no)	X	
COPD severity based on GOLD assessment 	X	
mMRC breathlessness scale, completed by the patient	X	
Physical functioning (PF-10) questionnaire, completed by patient	X	X
General condition of patient evaluated by Physician's Global Evaluation (PGE)	X	X
Adverse Drug Reactions (serious and non-serious), fatal AE, pregnancy	X	X
Patient satisfaction with Spiolto ® Respimat ® , survey completed by the patient		X
Rational for Spiolto ® Respimat ® treatment discontinuation (if applicable)		X
Continuation or discontinuation of treatment with Spiolto ® Respimat ® after the study (yes/no)		X

 GOLD patient group (A, B, C or D) will be automatically calculated within the eCRF based on available exacerbation history, mMRC, and GOLD spirometric classification of airflow limitation based on post-bronchodilator FEV1 if available.

Baseline characteristics of patients being eligible and who gave Informed Consent, but were not treated in the study will also be collected.

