### **9.2.1 Selection of Patient Population**

1200 patients with chronic obstructive pulmonary disease (COPD) in whom combination treatment with long-acting bronchodilators is indicated in accordance with the guidelines are to be observed in approx. 225 sites (hospital and non-hospital pulmonary medicine physicians and general practitioners) as part of this NIS. In the six participating countries (Belgium, Denmark, Sweden, The Netherlands, Luxembourg and Portugal), sites in urban as well as rural areas will be included. The nationwide distribution of the participating sites in the six countries and the number of patients enrolled are intended to ensure that the data collected are representative.

Possible contraindications are to be checked prior to treatment with Spiolto® Respimat®. See also the latest Summaries of Product Characteristics on Spiolto® Respimat®.

Every physician is to enrol the first consecutive patients he/she chooses to treat with Spiolto® Respimat®. The inclusion of four to six patients is planned per site.

The decision to treat will be taken independently of participation in this NIS and will be made before participation is considered.

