### **9.3 VARIABLES**

During the observational period, the following data will be collected in an eCRF:

- Patient demographics (age, gender, height & weight)
- Concomitant diseases / Comorbidities such as cardiovascular disease, diabetes mellitus, musculoskeletal impairment, renal diseases, liver diseases, osteoporosis, gastroesophageal reflux (GERD), or lung cancer
- COPD related and other relevant concomitant medication such as beta-blockers, beta-agonists, corticosteroids, or proton pump inhibitors
- General condition of patient based on Physician's Global Evaluation (PGE) to assess the general condition of the patient at the beginning and at the end of the study
- Smoking status (current smoker, former smoker, and never smoker) and pack-years
- Reported exacerbations based on medical history in the last 12 months and exacerbations leading to hospitalization in the last 12 months
- Assessment of the severity of breathlessness based on the Modified Medical Research Council Questionnaire (mMRC score)
- Physical Functioning based on PF-10 scores
- Patient satisfaction with Spiolto® Respimat® to assess the overall satisfaction with Spiolto® Respimat® as well as specific inhalation from the device and device handling
- Safety Reporting; Adverse Drug Reactions (serious and non-serious), fatal AEs, pregnancies at the beginning and at the end of the study
- GOLD spirometric classifications (1, 2, 3, 4), based on GOLD guidelines
- GOLD patient groups (A, B, C, D), based on GOLD guidelines

\*The PF-10 is a sub-domain of the SF-36 and consists of 10 questions evaluating the extent of experienced restrictions while conducting usual activities. Each question of the PF-10 can be answered with "yes, limited a lot", "yes, limited a little", or "No, not limited at all", with a score of 1, 2, or 3. The scores over the 10 questions will be summed, resulting in a value between 10 (a patient answering all questions with "yes, limited a lot") and 30 (a patient answering all questions with "No, not limited at all"). The final sum of the individual scores will be standardized to a range of 0 to 100 using the following formula:  $100 * (\text{sum} - 10) / 20$ .

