#### 9.10.1.3.1 Source Documents

Source documents provide evidence for the existence of the patient and substantiate the integrity of the data collected. Source documents are filed at the investigator's site.

Data entered in the eCRFs that are transcribed from source documents must be consistent with the source documents or the discrepancies must be explained. The investigator may need to request previous medical records or transfer records; also current medical records must be available.

For the eCRF, the following data must be derived from source documents:

- Patient demographics (age, gender, height, and weight);
- History of smoking
- Reported exacerbations
- Past COPD therapies (6 months before visit 1)
- Respimat® training (Yes/No)
- GOLD spirometric classification (1,2, 3, 4)
- GOLD patient groups (A, B, C, D)
- Concomitant diseases / Comorbidities
- Concomitant COPD and other relevant medication
- Breathlessness based on mMRC score
- Physical Functioning (PF-10) Questionnaire
- Patient Satisfaction Questionnaire
- Adverse Drug Reactions (ADR & SADR), fatal AEs, pregnancies
- Rational for Spiolto® Respimat® treatment discontinuation (if applicable)
- Details of treatment continuation / discontinuation

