7.7 SAFETY ANALYSIS

The analysis of adverse events will be descriptive and conducted according to Boehringer Ingelheim standards. The main focus will be on treatment emergent events. All AE that occurred between start of treatment and 21 days after permanently discontinuation of therapy or end of study will be considered as treatment emergent and will be displayed in frequency tables. Non treatment-emergent events will be assigned to "screening" or "post-treatment" and only be displayed in listings. All analyses will be based on the treated set.

In context of the presented study, only drug-related adverse events or events with fatal outcome (i.e., serious adverse events) will be documented. Their frequency and severity will be tabulated according to MedDRA-SOC and PT. Serious events will be tabulated as well as adverse events (drug-related or serious ones) leading to treatment discontinuation. Moreover, the causality of events with fatal outcome will be displayed.

Unless otherwise specified, the analyses of drug-related adverse events and events with fatal outcome will be descriptive in nature. All analyses will be based on the number of patients with AEs and not on the number of events.

An overall summary of drug-related adverse events and events with fatal outcome will be presented.

The frequency of patients with drug-related adverse events or events with fatal outcome will be summarised by primary system organ class and preferred term. Separate tables will be provided for patients with serious adverse events.

The system organ classes will be sorted alphabetically, preferred terms will be sorted by frequency (within system organ class).

For analysis multiple AE occurrence data on the CRF will be collapsed into an AE event provided that all of the following applies:

- All AE attributes are identical (PT, NCI-CTC grade, action taken, therapy required, seriousness, reason for seriousness, relationship, outcome)
- The occurrences were time-overlapping or time-adjacent (time-adjacency of 2 occurrences is given if the second occurrence started on the same day or on the day after the end of the first occurrence). For classification into TEAE or Non-TEAE, the first documented start of event will be used.

For further details on summarization of AE data, please refer to [3] and [4].

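### Is entry to the treated set undefined for a patient who took Spiolto but never came back for Visit 2?

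*SAP*

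**What the plan says.** - **Set definition, SAP 6.3:** "Treated set (TS): All screened patients with informed consent, date of registration and at least one documented administration of" Spiolto Respimat. Baseline and safety tables use this set. Primary and secondary endpoints use the full analysis set (FAS), which also needs a PF-10 score at both visits.
- **Set definition, Protocol 9.7.3:** the treated set is every patient who took one dose or more.
- **Timing, SAP 6.7:** Visit 1 covers history, demographics, registration and the initial examination. Spiolto treatment "will be documented at visit 2 after approximately 6 weeks of treatment".
- **Collected data:** Table 9.1:1, the list in Protocol 9.3 opening "During the observational period, the following data will be collected in an eCRF", and the list in 9.10.1.3.1 opening "For the eCRF, the following data must be derived from source documents" contain no Spiolto first-dose, start-date or stop-date item. Table 9.1:1 places the reason for discontinuation and the continuation item at Visit 2.
- **Untreated patients, Protocol 9.1:** "Baseline characteristics of patients being eligible and who gave Informed Consent, but were not treated in the study will also be collected".
- **Missing data, SAP 6.6:** apart from PF-10 items, "No other missing data will be imputed".
- **Safety window, SAP 7.7:** treatment-emergent events are "All AE that occurred between start of treatment and 21 days after permanently discontinuation of therapy or end of study". Other events appear only in listings.

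**The concern.** Read together, SAP 6.3 and 6.7 can be taken to mean that administration is documented only when the patient returns. A patient who took Spiolto and then stopped, was lost or died before Visit 2 would drop out of the treated set, although Protocol 9.7.3 would keep that patient.

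A Visit 1 record does not settle the matter. Consented patients who are never treated are also in the database. Protocol 9.2.1 says of the treatment choice: "The decision to treat will be taken independently of participation in this NIS and will be made before participation is considered". A decision is not a dose. The bar on imputation and the absence of an exposure analysis (SAP 7.6) offer no substitute.

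At stake are the denominators of the baseline and safety tables. Adverse drug reactions (ADRs) and fatal events are collected from consent onwards (Protocol 11.2), so an event may be known for a patient with no Visit 2. If such patients were counted while event-free non-returners were not, the ADR proportion would be too high. If all non-returners were left out, it could be too low. A missing start date could also decide whether an event is tabulated or only listed.

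**Working it through.** **The plan's own figures (Protocol 9.5).** Inputs: 1116 evaluable patients, 50% success, 7% drop-out.
- 1116 / (1 − 0.07) = 1200, as stated.
- 0.5 ± 1.96 × √(0.25/1116) = 0.5 ± 0.0293, or 47.1% to 52.9%, as stated.

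**How many patients.** 1200 − 1116 = 84. The documents do not split these into dosed non-returners, never-dosed patients and unusable PF-10 scores. The number concerned is therefore anywhere from 0 to 84, and the treated set would lie between 1116 and 1200 if every enrolled patient were dosed.

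**If all 84 are left out.** Let *a* be the ADR rate in returners and *b* the rate in the 84 (both assumed). The reduced set reports *a*; the full set gives (1116*a* + 84*b*)/1200.

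| *a* (reported) | *b* = 0% | *b* = 10% | *b* = 30% |
|---|---|---|---|
| 2.0% | 1.9% | 2.6% | 4.0% |
| 5.0% | 4.7% | 5.4% | 6.8% |

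For example, (0.05 × 1116 + 0.10 × 84)/1200 = 64.2/1200 = 5.35%. The reduced set overstates the rate when *b* is below *a* and understates it when *b* is above.

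**If only non-returners with an ADR are counted.** With *k* such patients, the inflation is 1200/(1116 + *k*), at most 1200/1116 = 1.075. An assumed true 5.0% would read at most 5.4%. If 42 patients are concerned, the limit is 1200/1158 = 1.036, and 5.0% would read at most 5.2%. No passage states this asymmetric rule.

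**Baseline tables.** If all 84 are left out, a mean shifts by (84/1200) × difference = 0.07 × difference. That is 0.7 points for an assumed 10-point PF-10 gap between returners and non-returners, and zero if they do not differ.

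**Does the text force any of these cases?**
1. SAP 6.7 says what is recorded at Visit 2. It does not say that nothing about treatment is recorded elsewhere.
2. Collecting baseline data on consented but untreated patients (Protocol 9.1) presupposes that they can be told apart from treated ones. Protocol 9.2 also requires a site log of all consented patients, treated or not.
3. SAP 5.4 includes therapy data among the collected variables. Protocol 9.7.3 lists respiratory treatment during the study among the data to be analysed. Neither names a first-dose date, but both show treatment data beyond the two Visit 2 items.
4. Protocol 9.4 has the first assessment before treatment begins. Visit 2 is about 6 weeks after Visit 1 (Protocol 8.2) and about 6 weeks after treatment start (SAP 5.1), so treatment starts at about Visit 1.
5. SAP 7.7 restricts recorded events to drug-related or fatal ones. A reaction attributed to Spiolto is itself evidence of a dose and cannot precede it. Table 11.2:1 in Protocol 11.2 ties fatal-event reporting to exposed patients, so the reporter must know exposure.
6. Protocol 9.7.4 requires every removal from the analysis to be documented with its reason, so non-returners could not be dropped unseen.

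**The case for a change.** The strongest argument for acting is that the plan leaves two readings open and does not choose between them. Patients who die or stop early can never supply a Visit 2 record, and they matter most for safety. With 30% ADRs among 84 non-returners, a set limited to returners would report 5.0% where the full set gives 6.8%. The remedy is also cheap: one sentence if the field exists, or a query for at most 84 patients if it does not. The SAP was final on 25 August 2017 and data collection was planned to March 2018, so there was time.

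It stands that neither document names the item that shows first administration or its date, and that the end of the treatment-emergent window needs a stop date that the lists do not show either. The harm does not follow. It needs an analyst to read into SAP 6.7 a restriction that is not there, to override the protocol's definition, and to ignore a recorded reaction as evidence of use. Protocol 9.6 leaves the specifications for data collection to the data management plan, and SAP 7.7 defers to sponsor standards for handling adverse events. None of these is among the documents, so silence here is weak evidence of a gap in the study.

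Two side points add little. Requiring a documented administration puts the protocol's definition into operation, since only recorded doses can be analysed, so its absence from SAP section 4 is not a hidden change. Discontinuation and continuation are categorical items, and the general tabulation rule in SAP section 7 is enough to produce them.

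**Conclusion.** No change is needed. The plan omits a detail that analysts fill sensibly. The rule for the treated set is stated in both documents; what is not stated is which data field shows that it is met, and that belongs with the eCRF and data management plan. A sentence naming the field would do no harm, but it would only write down what has to be settled in any case.

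The upper limit is 84 of 1200 patients, and it assumes that every planned drop-out was dosed and has no Visit 2. The effect on ADR proportions could go either way, and every figure for it rests on assumed rates. The primary and secondary endpoints do not change, because the FAS already excludes anyone without PF-10 at both visits. All analyses are descriptive (SAP section 7) and no hypothesis is tested (Protocol 9.7.2). The conclusion assumes that treated status is recorded for consented patients, as the protocol's separate handling of untreated patients implies. If the eCRF turned out to hold no such record, the status of non-returners would have to be obtained from the sites.
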